
mental health intervention to suggest conducting different studies in the recent systematic review by Akgün et al. (2019).

Accordingly, the primary aim of the current study is to test the efficacy of the online training program on mental health (DASS-21 and its subscales) regarding autistic traits. The secondary aim of the current study is to test the efficacy of the online training program on executive functions (working memory, inhibitory control, and cognitive flexibility), and social cognitive skills (cognitive empathy and affective empathy).

The following two hypotheses were addressed in the current study:

- 1. Online training on executive functions and social cognitive skills will promote mental health by reducing DASS-21 and its subscales scores in the current sample.**
- 2. Online training on executive functions and social cognitive skills will promote executive functions (working memory, inhibitory control, and cognitive flexibility) and social cognitive skills (cognitive empathy and affective empathy) in the current sample.**

[figure not shown]
Methods Study Design

The present study adopted a multifactorial design including pretest and posttest conditions to test the efficacy of combined EFs and social cognition online training via computers, tablets, or smartphones for mental health symptoms (depression, anxiety, and stress) in the experimental and control groups. Multifactorial design also called mixed design refers to including both within- participant design (testing the same participants over time) and between-participant design (comparing different groups, Breakwell et al., 2012). The independent variable for this study is online training while the dependent variables are mental health scores (depression, anxiety, and stress symptoms), executive functions (cognitive flexibility, inhibition, and working memory), and social cognition (cognitive empathy and affective empathy). According to our previous findings

(Chapter 4), autistic traits are included in this study as covariates, which are defined by characteristics that might affect the study's outcome (Cambridge University Press, n.d.).

Participants

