To measure autistic traits, the Autism Quotient (AQ; Baron-Cohen et al., 2001) was used. AQ for adults is adapted to Turkish culture by Köse and colleagues (2010). The self-report questionnaire consists of 50 questions using a Likert-scale rating; “definitely agree”, “slightly agree”, “slightly disagree”, and “definitely disagree”. In the Turkish adaptation of the AQ for adults, Cronbach’s alpha value for this scale is .64, and test-retest reliability is $r = .72$. The AQ is a widely used assessment tool that measures five subscales: social skills, communication, attention to detail, attention switching, and imagination. It is available in different languages (e.g., Turkish by Köse et al., 2010; Dutch by Hoekstra et al., 2008; Japanese by Wakabayashi et al., 2006).

Depression Anxiety Stress Scale 21(DASS – 21; Lovibond & Lovibond, 1995; Sarıçam, 2018)

DASS-21 is a self-report scale to examine depression, anxiety, and stress levels for adults by Lovibond and Lovibond (1995). The Turkish adaptation study for DASS-21 was conducted by Sarıçam (2018). This scale consists of three subscales, one for depression, one for anxiety, and one for stress. The total number of items is 21. For this scale, inter-scale reliability with Cronbach’s Alpha is .87 for depression, .85 for anxiety, and .81 for stress subscales. Test-retest reliability is $r = .68$ for depression, .66 for anxiety, and .61 for stress.

Performance Tasks

It was administered the following performance tasks to evaluate executive functions such as cognitive flexibility, WM, and inhibitory control, as well as social cognition including cognitive empathy and affective empathy. To ensure standardized measurement, we recorded the errors for each task based on previous intervention studies (Chooi & Logie, 2020; de Vries et al., 2015;

Macoun et al., 2021; Maraver et al., 2016). Each task begins with a non-scored trial to ensure that participants understand the task before scoring begins. The only exceptions are for the self-assessment manikin for affective empathy, and the Eyes Test for which detailed information was provided.

Wisconsin Card Sorting Task (WCST; Berg, 1948)

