completion of the research studies, the control group (on the waiting list) is scheduled to access the online training program in accordance with ethical guidelines.

Data Analysis

The data from the current study was analyzed using the SPSS 25.0 package. Initial analyses were performed to determine if the data showed a normal distribution. Before conducting parametric tests, the Shapiro-Wilk test, box plots, and skewness and kurtosis scores were used to check for normal distribution. The self-report questionnaires' data was found to be normally distributed according to the Shapiro-Wilk test ($p > .05$). As for the performance tasks, the skewness and kurtosis of the data fell within an acceptable range for applying parametric tests, as specified by Hair and colleagues (2010). Covariate analyses were conducted to account for the effects of autistic traits in the intervention model. Before including covariates in the analyses, correlation analyses and tests for homogeneity of regression slopes were performed according to the assumptions of covariance (Field, 2013). The results showed that only communication and attention-switching had significant correlations with dependent variables ($p < .05$) and met the assumptions for being used as covariates for mental health symptoms (Field, 2013). Regarding EFs and social cognitive skills, communication, attention to detail and imagination entered as covariates in the model ($p < .05$); however, only communication met the assumptions for homogeneity of regression slopes for EFs and social cognitive skills (Field, 2013). All correlation tables for these assumptions were presented in Appendix C, D, and E. Moreover, t-test analysis was carried out to see whether the pretests of dependent variables and AQ and its subscales for experimental and control groups

differ. Due to more than 8 variables; a conservative p -value was set ($p = .01$). The results showed no significant differences in all pretest scores and AQ (all $ps > .01$).

In the experimental study, 2 x 2 mixed design repeated measure ANOVAs were conducted to examine the group (experimental and control group) and the effects of time (pretest and posttest) on mental health (DASS-21 and its subscales), as well as executive functions (working memory, inhibitory control, and cognitive flexibility), and social cognitive skills (cognitive empathy and affective empathy). In terms of performance tasks, to ensure standardized measurement, errors

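### The AQ covariates are chosen from the trial's own outcome correlations, differ between the two hypotheses, and no adjusted or unadjusted model is named as primary

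*Combined protocol and SAP*

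**What the plan says.** Under Study Design, citing the group's earlier findings, the plan states that "autistic traits are included in this study as covariates". It does not say whether this means the AQ total or its subscales. The AQ description under Materials says that the instrument "measures five subscales: social skills, communication, attention to detail, attention switching, and imagination".

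The Data Analysis section gives the aim: "Covariate analyses were conducted to account for the effects of autistic traits in the intervention model". Candidates were screened by correlation with the dependent variables and then by a homogeneity-of-slopes test. For mental health, "only communication and attention-switching had significant correlations with dependent variables" and met the assumptions. For executive functions and social cognition, "communication, attention to detail and imagination entered as covariates in the model", yet "only communication met the assumptions for homogeneity of regression slopes for EFs and social cognitive skills". The text does not say whether attention to detail and imagination were then removed.

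The section ends with the main model: "2 x 2 mixed design repeated measure ANOVAs were conducted to examine the group" and time effects on every outcome. That sentence names no covariate. Nothing says which result, adjusted or unadjusted, answers each hypothesis.

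**The concern.** A covariate included on prior grounds should be fixed before the outcomes are seen. Here the set is settled by p < .05 correlations in the same 65 people who supply the efficacy result. The screen is uncorrected over five subscales and about nine outcomes (DASS-21 total and three subscales, three executive measures, two social measures). The same section tightens its pretest comparisons to p = .01 because of the number of variables, but leaves the covariate screen at .05.

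Two things are at stake. The adjusted effects under hypotheses 1 and 2 are conditioned on different traits, so they do not mean the same thing. And because no primary model is named, a reader cannot tell which of several available p-values is the confirmatory one.

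**Working it through.** The plan gives no figure for the covariate step, so there is none to reproduce. Its sample size of 44 is not an input here. (With f = .25, power .80 and alpha .05, it is obtained only at a pre-post correlation of about .34 to .36, which is not stated.)

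**Inputs from the documents:** 31 + 34 = 65 analysed (Participants); five AQ subscales (Materials); screening level .05 (Data Analysis); DASS-21 test-retest r of .61 to .68 (Materials), used as a guide to the pre-post correlation. **Assumed:** pre-post correlation .65, correlation between subscales .3, subscale-outcome correlations 0 to .3, screening on posttest scores, and allocation unrelated to AQ.

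1. *Passing threshold.* With t = 1.998 on 63 df, critical r = t / √(t² + 63) = 1.998 / √66.99 = .244.

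2. *Chance hits when no subscale is related to anything.* P(at least one) = 1 − .95^k. For 5 x 1 tests, k = 5 gives .23. For five subscales and four DASS-21 scores, k = 20 gives .64. Independence is assumed, so these are upper guides. Simulation with correlated outcomes gave .43 (one time point) to .62 (both) for the three DASS-21 subscales, and .68 to .87 for the five executive and social outcomes.

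3. *Stability of the set.* A subscale with true r of .2, .25 or .3 passes with probability .36, .52 or .68. With true r of .2 to .3 for all five, two identical trials select the same set only about 6 to 8% of the time.

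4. *Effect on group x time.* With two time points this is a test of change. The unadjusted SE in outcome SD units is √(2(1 − .65)) × √(1/31 + 1/34) = .837 × .248 = .208, which the simulation matches. Results from 5,000 simulated trials per cell, for one outcome:

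| r with pretest / posttest | Type I error, unadjusted / screened | SE, unadjusted / screened | Verdict differs, no effect | Verdict differs, 0.5 SD effect |
|---|---|---|---|---|
| 0 / 0 | .053 / .053 | .207 / .207 | 0.4% | 0.9% |
| .2 / .2 | .046 / .045 | .207 / .210 | 1.1% | 4.1% |
| .3 / .3 | .055 / .052 | .207 / .213 | 1.7% | 6.3% |
| .1 / .3 | .050 / .051 | .207 / .200 | 3.6% | 11.2% |

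5. *Free choice.* If any of the 2⁵ = 32 subscale sets may be reported, the null rejection rate is about .08 to .10.

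6. *A fixed AQ total.* Added to the same change model, it holds type I error at about .05. Its SE is no larger than the screened model's when the traits are related to outcome: .208 against .212 in the .3 / .3 case, and .195 against .200 in the .1 / .3 case.

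7. *Level or change.* Correlation of a trait with change = (r_post − r_pre) / √(2(1 − ρ)), where ρ is the pre-post correlation. For .3 and .3 it is 0. For .1 and .3 it is .2 / √.7 = .24. A trait equally related to both time points therefore cannot sharpen group x time, as the .3 / .3 row shows.

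**The case against.** The strongest defence is that the described procedure does little damage. It is a two-step rule, not a free search, and type I error under it is nominal. The high chance-hit rates assume AQ is unrelated to every outcome, whereas the covariate was included because of earlier findings. The ANOVA sentence names no covariates, so unadjusted results may already be reported. All of this stands, and it limits the size of the point. It does not supply the missing statement of which model is primary, and it does not make the two covariate sets comparable.

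A reader might go further and infer that the analysis fails to adjust for autistic traits as the design promises. The documents do not support that. Study Design speaks of covariates in the plural and specifies neither the total nor any subscale, so adjusting for subscales is within its wording.

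A reader might also infer that the screen used the wrong quantity, score level instead of change. That is the natural reading, since the dependent variables are defined as scores, but it is not stated, and the correlation tables are in appendices that were not available. The argument holds only if levels were screened and the correlations with pretest and posttest are similar. It then applies equally to the AQ total, so it limits what any AQ covariate can add.

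Finally, a covariate fixed now is itself chosen after the data were analysed. That is true, and the report should say so.

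**Conclusion.** The concern holds as a shortcoming of specification with a modest effect on inference. Adjustment for autistic traits is partial, differs between hypotheses 1 and 2, and rests on a selection that would often come out differently in a repeat of the same trial. The group x time test is not invalidated. The mechanical rule leaves type I error at about .045 to .053; about 8 to 10% arises only if the model can be chosen freely. The significance verdict differs from the unadjusted test in roughly 0.4 to 3.6% of trials with no effect and about 1 to 11% with a 0.5 SD effect.

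It would be too strong to say that the adjusted results as a whole depend on chance: that describes the covariate set, and reaches the treatment estimate only to this smaller degree. The figures rest on the assumed correlations and on allocation being unrelated to AQ among those analysed. With 65 of 178 randomised participants analysed (37%), that last assumption is not assured.

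**What to change.** - Drop the outcome-correlation screen. Use one covariate set for every outcome, chosen without reference to the trial's outcomes. The pretest AQ total is a sensible example, which Study Design allows but does not specify.
- Name either the unadjusted or the fixed-covariate group x time test as primary, and report the other beside it.
- State whether attention to detail and imagination stayed in the executive and social models, and whether pretest, posttest or change scores were screened.
- Label the existing subscale-adjusted models data-driven and post hoc. Describe the re-run as specified after the fact too.
- If the time main effect is interpreted from a model containing AQ, mean-centre AQ first. This leaves group x time unchanged.

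The cost is re-running models on data in hand and a paragraph of text. The statistical price is one degree of freedom, and a slightly weaker covariate if only one subscale is prognostic.

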A power analysis (G*Power) was conducted to determine the number of participants needed to achieve this goal. For repeated measures analyses, 44 participants are required in order to reach a medium effect size of .25 with an adequate power of .80 at $\alpha = .05$ (Faul et al., 2009) to determine interaction effects of between and within participants' factors. Convenience sampling via advertisement through social media, mail groups, and on campuses was used to collect participants. Initially, 178 adult participants were recruited for this study to reach adequate power for multivariate analysis. Participants randomly and equally were assigned to the experimental group (89 participants) and control group (89 participants) to see whether the combined training program was effective for the general population. 33 participants for the experimental group and 48 participants for the control group completed the posttest. However, after checking outliers and normality analysis, 31 participants for the experimental group (28 female, 3 male), and 34 participants for the control group (29 female, 5 male) were included in the further analyses. Please see the figure 6.1. the flow of participants through each stage of the study. The details of the participants were presented the Table 6.1. Demographic Characteristics. To reduce drop-out, incentives such as drawing for money/prizes were used. Inclusion criteria for adult participants are being aged 18 or above, being able to use computers, smartphones, or tablets, being native Turkish citizens, having no record of any psychiatric disorders, and having no record of any physical and neurological conditions that prevent to use of technological devices. Participants who are under the age of 18 and have any record of psychiatric and physical conditions that prevent to use of technological devices were excluded from the study.

Materials

Self-Report Questionnaires

Figure 1. The Flow of Participants

Demographic Information Form

Basic information such as age, gender, education level (i.e., undergraduate, postgraduate), and income was obtained from the participants, and it was developed by the researcher.

Autism Quotient (AQ) for Adults Turkish Version (Baron-Cohen et al., 2006; Baron-Cohen et al., 2001a; Köse et al., 2010)

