and-white photographs of human eyes. For each photograph, participants were asked to choose which of 4 words best describes what the person in the photograph is feeling or thinking. The version used was adapted for Turkish by Girli (2014). The Cronbach alpha internal consistency coefficient for this test is greater than .70. Accuracy of the test was measured.

Self-Assessment Manikin (SAM; Bradley & Lang, 1994)

Self-Assessment Manikin was carried out to measure self-reported emotional responses to facial expression images for affective empathy. Karolinska Directed Emotional Faces (KDEF, Conley et al., 2018; Lundqvist et al., 1998) were used to express facial emotions. In total, 30 images (15 male, 15 female) were chosen and seven emotional expressions including happiness, neutral, anger, fear, and disgust were depicted. The task requires participants to examine each facial expression and rate how they feel it on a valence scale (more negative (1) to more positive (9)). The tasks were adapted from Wai and Tiliopoulos (2012). Valence scores for each emotion were obtained by summing responses for all images.

Procedure

Approval from the ethical committee of Ibn Haldun University was obtained for this study (No. E-71395021-050.06.04-34359) and the protocol ID of clinical trials was obtained (NCT06213194). The participants for the study were recruited using convenience sampling through advertisements on social media, mail groups, and campuses. Once recruited, all participants completed pretest questionnaires and tasks before assigning them to the groups and undergoing training on the *MindZone* training website (www.mindzone.com.tr). 31 participants

for the experimental group (28 female, 3 male), and 34 participants for the control group (29 female, 5 male) were included for the study. The experimental group underwent an online 6-week training period through the website developed by the researcher (www.mindzone.com.tr), while the control group was placed on a waiting list. Posttests were collected at the end of the 6th week from both experimental and control groups. Additionally, the researcher and research assistant checked each participant's progress weekly, sent reminder messages, and made phone calls to improve training continuity if participants had not completed the requirements. Details about training are presented in Table 5.2. *MindZone* Manual (see Chapter 5). After the

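### Four primary DASS-21 scores are tested separately with no stated success rule, lead score, deciding effect or multiplicity correction

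*Combined protocol and SAP*

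**What the plan says.** The aims in the Introduction rank the outcomes: "the primary aim of the current study is to test the efficacy of the online training program on mental health", with the DASS-21 and its subscales given as the measure. Executive functions (three outcomes) and social cognitive skills (two) are secondary. Hypothesis 1 expects training to "promote mental health by reducing DASS-21 and its subscales scores in the current sample". Study Design is narrower: "the dependent variables are mental health scores (depression, anxiety, and stress symptoms", with no mention of the total.

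Participants gives the only alpha linked to efficacy, .05, in a sample-size statement of 44 whose purpose is "to determine interaction effects of between and within" participants' factors. It adds that 178 were recruited "to reach adequate power for multivariate analysis".

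Data Analysis describes separate mixed ANOVAs of group by time for every primary and secondary outcome. It states no significance level for them, no correction and no order of testing. Its one stricter threshold, "Due to more than 8 variables; a conservative p -value was set" (.01), belongs to the pretest comparison of the arms, and the sentence that follows reports the result of that comparison.

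For affective empathy, Materials says "Valence scores for each emotion were obtained by summing responses for all images", while the end of Data Analysis says only that summed image scores were entered.

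**The concern.** With four scores and no rule, hypothesis 1 could be declared supported when one score is significant, when a chosen score is, or only when all are. These rules have different error rates, and the text does not say which was used.

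The rule can also decide the conclusion. If training changes only one subscale by the planned effect size, an any-one rule would succeed in about 94-98% of trials and an all-four rule in about 1%.

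Two further gaps compound this. A group-by-time ANOVA yields three effects (group, time, interaction), and Data Analysis does not say which one decides; Participants names the interaction only for power. The size of each family is also open: three or four primary scores, and five to nine secondary ones.

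**Working it through.** **Inputs from the documents.** Planning alpha .05, effect size .25 (read as Cohen's f), N = 44; analysed 31 + 34 = 65 (Participants). Three DASS subscales, with test-retest values .68 "for depression, .66 for anxiety, and .61 for stress" (Materials). **Assumed, because not given:** correlations between the DASS change scores, and the pre-post correlation rho used for power.

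**1. The plan's own figure.** For a two-group, two-time interaction, lambda = f² × N × 2/(1 − rho), with 1 and N − 2 degrees of freedom. With rho = .35: .0625 × 44 × 2/.65 = 8.46, power .81. So 44 is reproduced at rho of about .35. With rho = .5, 34 would be enough.

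**2. Family sizes.** Primary: total + 3 subscales = 4 (or 3 under Study Design). Secondary: 3 + 2 = 5. If each of the five emotions named in Materials is a separate score: 4 + 5 = 9.

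**3. Error rates when no DASS score is affected.** Simulated normal statistics for three equally correlated subscales, with the total as their sum, each tested at two-sided .05:

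| Assumed correlation | Any one, either direction | Any one, benefit only | All four, either direction | Holm across four, either direction |
|---|---|---|---|---|
| 0 | 16.1% | 8.3% | <0.01% | 4.4% |
| .3 | 14.4% | 7.2% | 0.1% | 4.0% |
| .5 | 13.0% | 6.5% | 0.3% | 3.6% |
| .8 | 9.9% | 4.9% | 1.4% | 2.7% |

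Against a nominal 2.5%, false benefit under the any-one rule is 4.9/2.5 = 2.0 to 8.3/2.5 = 3.3 times as frequent. With only the three subscales, the any-one rate in either direction is 12.5% at .5 and 9.8% at .8.

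**4. All-four rule when some scores do improve.** With two subscales truly improved (noncentrality √12.5 = 3.54 to √16.25 = 4.03, the planned effect at N = 65) and one not, all four are significant for benefit in about 2.5% at correlations .5-.8. This is nominal, so no correction is needed.

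**5. Secondary family, any one at .05.** Five independent tests: 1 − .95⁵ = 22.6%, falling to 14.8% at an assumed correlation of .7. Nine independent tests: 1 − .95⁹ = 37.0%.

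**6. Power cost of the strictest Holm step, .05/4 = .0125.** In a 2 × 2 interaction, f = .25 is a between-arm difference in change of 4 × .25 = 1.0 SD. Check at N = 65, rho = .35: N × d²/(8(1 − rho)) = 65/(8 × .65) = 12.5, and .0625 × 65 × 2/.65 = 12.5. Power for one score with rho .35-.5:

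| True difference in change | at .05 | at .0125 |
|---|---|---|
| 1.0 SD | 94-98% | 83-92% |
| 0.5 SD | 41-51% | 22-30% |
| 0.32 SD | 20-25% | 8-11% |

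The last row uses the .32 that the Introduction quotes for digital interventions in autism.

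**7. Pretest adjustment.** With equal variances, error variance is proportional to 1 − r² after adjustment and to 2(1 − r) for change, a ratio of (1 + r)/2. At r = .61 this is .805 and at .68 it is .840, so 16-20% lower. At .35-.5 it is .675-.750, so 25-32% lower.

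**The case against.** The strongest defence is that hypothesis 1 names the total and the subscales together. Read as requiring all of them, it inflates nothing. This stands as a possible reading. But it is an expected direction of effect, and Data Analysis does not turn it into a decision rule.

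A second defence is that the reference to multivariate analysis implies an omnibus test acting as a gate. That phrase supports the recruitment target only; no omnibus test is described.

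A third is that primary and secondary outcomes are already ranked. They are, but the gap lies within each family.

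Some stronger readings are not supported:

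- A reader might infer that the reported primary error rate is inflated. That follows only under an any-one rule, which the text does not state, and its size rests on assumed correlations. The documents show no efficacy p-values.
- A reader might infer from the .01 pretest threshold that an imbalance was hidden. A stricter threshold does make it easier to declare no difference, but no actual imbalance is shown.
- A reader might infer that Holm would usually detect an effect confined to one subscale. This holds at 1.0 SD and fails at 0.5 SD.
- A reader might take an all-four rule to be always well below nominal. That is so only when no score is affected.

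**Conclusion.** The concern holds as a gap in the decision rule and should be fixed. Four primary and five to nine secondary scores are tested with no success rule, lead score, correction or named deciding effect. Under an any-one rule, false benefit on the primary aim is about 5-8% against 2.5%. This is illustrative, for assumed correlations of .8 down to 0 between change scores, with the total as the sum of the subscales. Under an all-four rule it is at most about 2.5%. What is established is that the error rate of the primary claim cannot be determined from the text, not that it was exceeded.

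**What to change.** In Data Analysis:

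1. Name the group effect that decides each hypothesis: the interaction or, under item 4, the adjusted group difference.
2. If an all-scores rule or a lead score was documented before outcome data were seen, state it and follow it. An all-scores rule needs no correction; a lead score is tested first at .05, then Holm across the rest. Otherwise report Holm-adjusted p-values across the four DASS scores beside the unadjusted ones, labelled post hoc, because the analyses are already described as done.
3. List every secondary score tested, including how many affective-empathy scores there are. Apply Holm or false discovery rate control within that list, or label the results exploratory.
4. For precision rather than multiplicity, analyse posttest adjusted for pretest instead of the group-by-time contrast. The 16-20% reduction in error variance assumes that the test-retest values in Materials hold over six weeks in this sample.

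Cost: no new data, a rerun, and one degree of freedom for the pretest covariate. Under Holm the smallest DASS p-value must be at or below .0125. For the group-by-time test of a single score, power then falls from 94-98% to 83-92% at 1.0 SD and from 41-51% to 22-30% at 0.5 SD, so some results may lose significance. Item 4 recovers part of this loss.

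### Non-significance at p = .01 is taken as showing that the arms did not differ at pretest; the lower threshold makes this check more lenient, and no threshold would make it evidence of comparability

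*Combined protocol and SAP*

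**What the plan says.** All places are in the Combined protocol and SAP.

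- **Data Analysis.** The check is described thus: "t-test analysis was carried out to see whether the pretests of dependent variables and AQ and its subscales for experimental and control groups" differed. The number of variables, more than eight, is given as the reason why "a conservative p -value was set ($p = .01". The conclusion is "The results showed no significant differences in all pretest scores and AQ", supported only by the statement that every p exceeded .01. The text gives no effect sizes or intervals and does not say which participants were tested.
- **Participants.** 178 people were assigned 89:89, and "33 participants for the experimental group and 48 participants for the control group completed the posttest". After outlier and normality checks, 31 and 34 were kept for further analyses.
- **Procedure.** The pretest preceded allocation: "all participants completed pretest questionnaires and tasks before assigning them to the groups".
- **Data Analysis, main model.** Outcomes are tested by 2 x 2 group-by-time mixed ANOVAs. The only covariates named are AQ subscales.

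**The concern.** The t-tests are the only check of pretest comparability described in the text. Lowering alpha from .05 to .01 protects against wrongly declaring a difference. In this check the favourable conclusion is that there is no difference, so the same step makes the check easier to pass. A DASS-21 pretest difference with p between .01 and .05 would be reported as absent.

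The more general fault is that a non-significant test is used as evidence of similarity. With arms of about 30, the test cannot exclude imbalances large enough to matter.

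Randomisation does not fully protect the analysed groups. Loss before the posttest differed by arm, and so did removal of completers afterwards. The group-by-time term of a 2 x 2 mixed ANOVA is a comparison of change scores, so a chance pretest imbalance enters it through regression to the mean and could imitate a training effect or hide one.

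**Working it through.** **Plan's own figure.** For this check the plan states only the threshold, p = .01. It gives no detectable difference, so there is nothing to reproduce.

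**Inputs.** Arm sizes 89/89, 33/48 and 31/34 (Participants); alpha .01 (Data Analysis); DASS-21 test-retest r of .68, .66 and .61 (DASS-21 paragraph under Materials). Assumption: two-sided independent-samples t-tests, since sidedness is not stated.

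**1. Largest observed difference that passes.** In SD units this is t(1 - alpha/2, n1 + n2 - 2) x sqrt(1/n1 + 1/n2).

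| Sample tested | SE (SD units) | t at .01 | Limit at .01 | Limit at .05 |
|---|---|---|---|---|
| 31 v 34 | 0.248 | 2.656 | 0.66 | 0.50 |
| 33 v 48 | 0.226 | 2.640 | 0.60 | 0.45 |
| 89 v 89 | 0.150 | 2.604 | 0.39 | 0.30 |

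In every row the .01 limit is wider than the .05 limit, so the direction of the error does not depend on which sample was tested.

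**2. Chance of flagging a true imbalance (noncentral t, 31 v 34).** A true 0.5 SD difference is flagged 27% of the time at .01 and 51% at .05. A true 0.66 SD difference is flagged about half the time at .01. The 0.66 SD limit therefore applies to the observed difference, not the true one.

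**3. Selection between assignment and analysis.**

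- No posttest: 89 - 33 = 56 of 89 (63%) in training; 89 - 48 = 41 of 89 (46%) in control; Fisher p = .035.
- Completers removed: 33 - 31 = 2 of 33 (6%) in training; 48 - 34 = 14 of 48 (29%) in control; Fisher p = .011.
- Not analysed in total: 58 of 89 and 55 of 89. The similar totals hide two different routes out of the analysis.

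**4. Possible effect on the change contrast.** For a chance imbalance d, with equal SDs and pre-post correlation r, the expected shift in the difference in change is (1 - r) x d.

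- At the .01 limit: (1 - .68) x 0.66 = 0.21 SD; (1 - .61) x 0.66 = 0.26 SD.
- At the .05 limit: (1 - .68) x 0.50 = 0.16 SD; (1 - .61) x 0.50 = 0.19 or 0.20 SD (0.19 with the unrounded limit of 0.496).

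Using .01 in place of .05 thus adds about 0.05 to 0.06 SD to the possible shift. The larger part comes from relying on a significance test at all.

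**The case against.** **The threshold has a reason.** With nine independent tests at .05, the chance of at least one false flag is 1 - .95^9 = 37%. The rule is therefore a multiplicity adjustment and not arbitrary. That stands as an explanation, but it does not suit this use: fewer false alarms are bought with less ability to see real imbalance.

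**The sample is not stated.** A reader might infer that the check was run on the 31 and 34. The Participants section makes that plausible, but the Data Analysis section does not say so, and the limit could be as low as 0.39 SD. If all 178 were tested, however, the result does not describe the 65 analysed. Nor does the plan say that the t-tests were meant to address withdrawal.

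**The shift is a ceiling.** A reader might set 0.21 to 0.26 SD against the d = .32 cited in the Introduction and conclude that most of a plausible effect could be artefact. The documents do not support that. No imbalance of this size is shown, and .32 comes from digital interventions in ASD, whereas this sample had no recorded psychiatric disorder. The planned f of .25, in the usual within-between parameterisation, is a difference in change of 4 x .25 = 1.0 SD, against which the ceiling is 21 to 26%.

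**The formula has limits.** It assumes that both arms regress to a common mean. If stayers differ on a stable trait, each arm regresses to its own mean and the contrast need not shift by this amount.

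**Absence is judged from the visible text.** The flow figure and Table 6.1 are not shown. The text describes Table 6.1 as demographic and Appendices C to E as correlation tables, so neither is said to compare leavers with stayers, but it cannot be ruled out.

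**Conclusion.** The point holds. Reading p > .01 as no pretest difference is not sound: lowering alpha weakens a comparability check, and returning to .05 would not repair it. The observed imbalance that could pass is between 0.39 SD (89 v 89) and 0.66 SD (31 v 34), assuming two-sided tests.

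The consequence for the DASS-21 group-by-time contrast is a possible shift of at most 0.21 to 0.26 SD. That requires the 31 v 34 sample, a chance imbalance at the limit, and r of .61 to .68 over six weeks. The documents do not show that such a shift occurred; nor do they let a reader exclude it, because only p > .01 is given. Unequal loss and unequal removal of completers make the question worth answering from the pretest data.

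**What to change.** - Drop the p = .01 rule and the conclusion of no difference drawn from it.
- State which participants the pretest comparison covers.
- Report standardised pretest differences between arms, with confidence intervals, for each DASS-21 score, each task, and the AQ and its subscales: once for the 89 + 89 assigned and once for the 31 + 34 analysed. The 95% half-widths will be about 0.30 and 0.50 SD, which shows how little the smaller set can exclude.
- Within each arm, compare pretest scores of three groups: those without a posttest (56 and 41), completers who were removed (2 and 14), and those analysed (31 and 34). A simple split by posttest completion would count the 16 removed completers as stayers.
- Add a sensitivity analysis that adjusts every outcome for its own pretest score (ANCOVA), whatever the observed imbalance. A trigger such as 0.25 SD is not advised: at 31 v 34 it is 0.25 / 0.248 = 1.01 standard errors, so chance alone exceeds it nearly one time in three per variable, and the choice of covariates would depend on the data. ANCOVA deals with chance imbalance; it does not by itself correct for selective loss.

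The cost is one table and one additional model per outcome, from data that should already be held because the pretest preceded assignment. The downside is that some differences now reported as absent may have to be shown.
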